lack of blinding. We will also ask the person performing clinical assessments to provide his/her best guess regarding treatment allocation at the final study to ascertain whether we were successful in maintaining a blinded assessor.

### **6.10. Assessment of Compliance**

Participants will be given a daily log to complete through the course of the study to allow assessment of compliance in applying the traction hand orthosis or the resting hand orthosis on a daily basis. Participants will be reminded to complete this daily log on a weekly basis by our Research Coordinator. We will ask the participants turn in the daily log at their final in person 24 week clinic visit.

Additionally, we will have our research assistant contact participants on a weekly basis via participants' preferred method of contact: email, text or phone to ask participants the following questions:

1. Do you feel the orthosis is helpful? (0 – 100)
2. Did you wear your hand orthosis this week? Y/N
3. (If the person did not wear the orthosis) – Why didn't you wear your orthosis?
4. How many times did you MISS wearing the orthosis this week?
5. (If there were days that the participant didn't wear the orthosis) – Why didn't you wear the orthosis every time?
6. On average, how long have you been wearing the orthosis each night? (number of hours)
7. Have you been completing your daily log? Y/N
8. Have you had any problems with the orthosis? Y/N – if yes, fill out adverse event form.

To maintain blinding of our Research Coordinator, we will not make specific mention of what kind of orthosis was used for each participant. These responses will be recorded in our main database. At the end of each contact point, we will also use this as an opportunity to remind participants to wear their orthoses every morning and night to increase the likelihood of effectiveness of the orthoses.

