#### **5.4 Screening Failures.**

Screen failures are defined as participants who consent to participate in the clinical trial but are not subsequently randomly assigned to the study intervention or entered in the study. A minimal set of screen failure information is required to ensure transparent reporting of screen failure participants, to meet the Consolidated Standards of Reporting Trials (CONSORT) publishing requirements and to respond to queries from regulatory authorities. Minimal information includes demography, screen failure details, eligibility criteria, and any serious adverse event (SAE).

Individuals who do not meet the criteria for participation in this trial (screen failure) because of insufficient pain, insufficient number of joints involved, pregnancy plans or status, or surgical plans may be rescreened. Rescreened participants should be assigned the same participant number as for the initial screening.

**5.5 Retention/Adherence Strategies.** Although hand OA is common, only a small portion of those with the problem seek medical attention for the problem. Thus, irrespective of the group allocation a participant is assigned to, most

participants are likely get a greater level of attention to their hand OA than if they did not participate in this study. So, participation in the study itself is likely a benefit to the participants.

Additionally, our research coordinator will contact the participants to provide reminders via email, telephone, or text messaging, based on participant preference, one week and one day before our follow up visits.

To increase adherence to application of the orthoses, we will provide daily reminders by providing each participant with a portable alarm clock that will remind participants approximately an hour before their bedtime and at the time of awakening, that they should don their orthoses and write in their log books.

Our research coordinator will also provide weekly email or text messages, based on participant preference, to our participants to remind them to wear their orthoses on a daily basis.

Another important contribution to good adherence will be the positive relationship that study personnel will have with the participants.

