## **6.3 Masking and Unmasking.**

Our Statistician, [name], and our research coordinator will only be aware of group designations of A and B. They will be blinded to treatment assignment. Prior to receiving treatment allocation information for the first participant of the study, our OT, [name] will flip a coin to assign whether treatment "A" represent traction orthosis or standard of care. She will keep this designation secret and will not share this designation with study staff or participants. Only our OT will be unblinded to treatment allocation. Opaque storage bags will be provided to the participants to store their orthoses. Our OT will make a specific point to tell the participants that they must store their orthoses in opaque bags when interacting with study staff. Masking will be maintained through the course of the study, during data collection, including when radiographs and MRIs are read and primary analyses are performed. Only when all primary data analyses are completed will our OT reveal which group is treatment "A" and unmask the treatment allocation.

Although we will make every effort to maintain blinding, it may be imperfect, where our research coordinator may accidentally have the treatment allocation revealed to him, by inadvertently seeing the orthosis or the participant might tell him which orthosis he/she received. Should this happen, , this will be viewed as a protocol deviation. Additionally,

we will make notation that our research coordinator may be unblinded to the treatment allocation. In those instances, we will have our alternate research coordinator who is still blinded, administer the treatment outcomes at the subsequent follow up visits.

Should the IRB, KAI, and/or our Safety Officer indicate a need to unblind the study prior to the end of data collection, [name] must confirm the need to unblind the study. Appropriate concerns that could be raised by any of these entities would include if there were unexpected or high numbers of SAEs that occurred in the study. [name] will instruct our OT to reveal which group is treatment "A" to our study statistician, [name], breaking the study blind. All intentional and unintentional blinding will be reported to the IRB, KAI and our Safety Officer.

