## **8.2. Symptom Efficacy Assessments**

All of the following assessments will be made by our Research Coordinator and itemization of the data will be collected in RedCap. These will include:

Outcomes: (Assessed at the baseline, week 4, week 12, and week 24 visits)

- the VAS pain scale, asking about pain in the hand that includes the most symptomatic DIP over the last 48 hours (primary outcome)
- Australian Canadian Hand OA Index (AUSCAN) pain scale, (although we have requested copyright permission to use the scale, we have yet to receive permission to do so – we plan to administer the outcome, but if not given permission, we will not publish with this data).
- the VAS pain scale, asking about pain in the most symptomatic DIP in the last 48 hours,
- the AUSCAN function subscale,
- the Functional Index for Hand Osteoarthritis (FIHOA)
- the Disabilities of the Arm, Shoulder, and Hand (DASH),
- the Michigan Hand Outcomes,
- the Functional Dexterity Test,
- grip and pinch strength, and
- tenderness on joint palpation on all hand joints.
- photographs of the participant's hands
- We will also take a medication inventory (dichotomous assessments)
  - i. Pain medications (e.g. acetaminophen, all non-steroidal anti-inflammatory medications, and opioid medications).
  - ii. Glucosamine and chondroitin
  - iii. Marijuana use

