All study data will be collected and managed using the REDCap electronic data capture tools, designed to comply with HIPAA regulations. This is a VA approved electronic data capture software. It is designed to support data capture for research studies from anywhere in the world with secure web authentication, data logging, and Secure Sockets Layer (SSL) encryption. It provides: 1) an intuitive *interface for validated data entry* 2) *audit trails* for tracking data manipulation and export procedures 3) *automated export procedures* for seamless data downloads to common statistical packages, an essential feature for data back-up and 4) user-friendly procedures for importing data from external sources. We will store all consent forms, all participant questionnaires, and study information on REDCap. On a weekly basis, all acquired information will be uploaded to a VA server on the VA network, protected by user login and passwords and we will run simple logic checks to assure the data is downloading appropriately. All servers are backed up daily to ensure data protection. Weekly full backups are stored in a vault at a secure remote location. The heart of the server system is a Hewlett Packard Itanium System running under the UNIX operating system. This server is used for managing and analyzing the large datasets. The Itanium server has four 1.5-gigahertz (GHz) Itanium central processing units (CPUs) that have instruction set architecture of 64 bit Intel microprocessors (IA64), 28.0 gigabyte (GB) of random access memory (RAM), and approximately 8 terabytes (TB) of disk storage. In addition to the Hewlett-Packard Itanium, six Dell servers run the Windows operating system, used for network applications, Structured Query Language (SQL) database, file sharing, and print sharing with a total storage capacity of 4TB.

All participants will be asked to turn in log books that are labeled with their study ID to our OT. In these log books, we will ask the participants to keep a daily log of when they apply and remove the orthoses, comfort level of the orthoses,

ease/difficulty of donning the orthoses, how well they like the orthoses, and overall hand pain using VAS scales. These data will be kept in a locked cabinet and the data will be transferred onto Red Cap to be managed in a similar manner that all the other clinic acquired data is managed.

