### **Data Download from RedCap**

Our Research Coordinator will download data from RedCap on a weekly basis once we initiate participant screening and this will continue until the last participant enrolled is seen at his/her last in clinic visit.

- This data will be stored on our M-drive folder under the “Data Collection/Red\_Cap” folder.
- Each download will be stored using the following naming convention: **RawDataHandRCT\_<YYYYMMDD>**.
  - In this naming convention , <YYYYMMDD> = year, month, date that the data was downloaded.

**Informed consent** is required by the BCM/MEDVAMC IRB to be obtained by reviewing a hard copy of the consent form and having the participant sign that hard copy. Our Research Coordinator will have this informed consent scanned and uploaded to the MEDVAMC electronic medical record system. Additionally, he will scan and upload another copy of the consent form on

- Our M-drive folder under the “Data Collection/Consent” folder.
- Each form will be stored using the following naming convention: **Consent\_<YYYYMMDD>\_<studyID>**.
  - In this naming convention:
    - <YYYYMMDD> = year, month, date that the consent was obtained
    - <studyID> = the participant’s study ID number.

**HIPAA form** is required by the BCM/MEDVAMC IRB to be obtained by reviewing a hard copy of the HIPAA form and having the participant sign that hard copy. Our Research Coordinator will have this HIPAA form scanned and uploaded to the MEDVAMC electronic medical record system. Additionally, he will scan and upload another copy of the form on

- Our M-drive folder under the “Data Collection/HIPAA” folder.
- Each form will be stored using the following naming convention: **HIPAA\_<YYYYMMDD>\_<studyID>**.
  - In this naming convention:
    - <YYYYMMDD> = year, month, date that the HIPAA form was signed
    - <studyID> = the participant’s study ID number.

A hardcopy of the **Daily Log** will be turned in by each participant at the 24 month visit. Our Research Coordinator will manually data enter all information from each daily log returned electronically into an Excel spreadsheet file stored in the same M:drive file listed above. We will make extra effort to verify that data recorded electronically will accurately reflect information derived from source documents.

- This data will be stored on our M-drive folder under the “Data Collection/Daily\_Log” folder.

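### The masked coordinator who makes the symptom and function assessments also handles reports that can reveal the orthosis, which puts the assessor-run secondary outcomes at risk

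*Combined protocol and SAP*

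**What the plan says.** Section 8.2 gives the symptom and function measures to one person: "All of the following assessments will be made by our Research Coordinator". Sections 6.2, 6.3 and 6.9 require that person to stay masked. Under 6.3 the statistician "and our research coordinator will only be aware of group designations of A and B", and only the occupational therapist (OT) knows what the labels mean.

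Section 6.10 sets weekly questions. Items 3 and 5 ask openly why the orthosis was not worn. Item 8 asks "Have you had any problems with the orthosis? Y/N – if yes, fill out adverse event form". On the caller it says "we will have our research assistant contact participants on a weekly basis", and then "To maintain blinding of our Research Coordinator, we will not make specific mention of what kind of orthosis was used for each participant". Section 5.5 says "Our research coordinator will also provide weekly email or text messages, based on participant preference".

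The coordinator has four further data tasks:
- **Adverse events.** The coordinator screens for them at clinic visits and receives reports between visits (8.7.b), records reportable events (8.7.g) and enters the data in REDCap (10.10.b).
- **Withdrawal and early-termination forms**, including the date and reason (7.1, 7.2).
- **Weekly REDCap downloads** (10.10.b).
- **Daily logs**, which allow free text (6.8): "Our Research Coordinator will manually data enter all information from each daily log returned electronically into an Excel spreadsheet file" (10.10.b). Section 10.7.b, however, says "All participants will be asked to turn in log books that are labeled with their study ID to our OT".

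**The concern.** The protection in 6.10 limits what staff say. It does not limit what a participant answers. Items 3 and 5 invite explanations, and in the traction arm the explanation may be the finger trap. Section 10.10.b lists trap-related skin, nerve and vascular complaints for the traction group only, and section 6.5 tells traction participants that a trap can be cut off.

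First disclosures are therefore likelier in the traction arm. An assessor who knows the allocation can influence effort-dependent tests and palpation, and the direction of that influence cannot be predicted. The remedy in 6.3, a change to a blinded alternate coordinator after a known disclosure, would then also change the assessor between visits more often in one arm than in the other.

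**Working it through.** The plan states no figure on this point, so the check sets its sections side by side.

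**1. Who asks the weekly questions?** Section 6.10 names a research assistant, a role that section does not define. Its next lines protect the coordinator's blinding in that same contact. Section 5.5 gives the coordinator weekly reminder messages, not the questions. Section 8.7.g has the investigator ask about adverse events on the weekly calls. The documents do not settle who asks.

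**2. Does the answer reach the coordinator anyway?** Yes, by several routes:

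| Route | Section | Why it can reveal allocation |
|---|---|---|
| Adverse event report and record | 8.7.b, 8.7.g, 10.10.b | Holds an event description and a field contrasting the two orthoses |
| Withdrawal and early-termination reason | 7.1, 7.2 | The reason may be the trap |
| Weekly download | 6.10, 10.10.b | Weekly answers are stored in the main database |
| Daily log keying | 6.8, 10.10.b | Free text |
| Weekly working meeting | 10.10.a | The coordinator attends a review that includes adverse event listings; the plan does not say whether they are shown by label |

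Sections 8.7.b and 8.7.g differ on who records adverse events, but in both the coordinator hears of them.

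**3. Do the safeguards block these routes?**
- Opaque bags (6.3, 6.4) hide the device, not a description of it.
- The request not to disclose (6.9) goes out with clinic-visit notices. No such wording accompanies the weekly questions or the log.
- The alternate coordinator (6.3) acts after a disclosure that someone recognises.
- The assessor's guess (6.9) is taken at the final visit only. It measures unmasking and does not prevent it.

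**4. Is log keying too late to matter?** For the participant who wrote the log, largely yes, because 6.10 has it returned at week 24 (10.10.b says 24 months, which conflicts). For others, no. Section 10.10.b has copies of entered logs stored weekly once the first is submitted. Twenty-four weeks is 24/52 × 12 = 5.5 months. If all data collection takes 18 months (4.3.b), the last participant could enter at about 18 − 5.5 = 12.5 months, well after the first log could return at about 5.5 months. Enrolment over 15 to 18 months (10.10.a) gives more overlap.

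**5. How far does one disclosure reach?** Section 6.3 gives the coordinator the A/B labels, and 6.2 has the allocation entered on REDCap. One disclosure linked to a label would identify both arms, so up to all 40 participants. Section 10.7.a can be read as sending the allocation to the OT only, which conflicts.

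**6. Which outcomes are exposed?** Dexterity, grip, pinch and palpation tenderness are run by the coordinator. The primary VAS is self-reported by participants who see their own orthosis. Radiographs and MRIs are scored by collaborators as a batch after the study (8.4.i, 8.4.iii).

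**7. Can a rate be given?** No. Section 8.7.e says expected events might be common, while 10.10.a calls them unlikely. Neither gives a figure. For an assumed disclosure probability p per contact, with independent contacts and the 20 reminder visits labelled in Table 1 (one of them in the week-12 visit window), the chance of at least one disclosure by a traction participant is 1 − (1 − p)^20:
- p = 0.1%: 2%
- p = 1%: 18%
- p = 5%: 64%

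For at least one disclosure among 20 traction participants (assuming 40 split equally), it is 1 − (1 − p)^400: 33% at p = 0.1% and 98% at p = 1%. These are chances of a disclosure, not of an unmasked assessment, because 6.3 moves recognised cases to a blinded alternate. The range is too wide to support an expected value.

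**The case against.** The strongest reply is that the plan takes masking seriously. It admits that blinding may be imperfect, treats disclosure as a protocol deviation, notes it, brings in a blinded alternate, uses opaque bags, asks participants not to disclose and tests the assessor's guess. Item 8 is a yes/no question, and discomfort, numbness or skin breakdown can be reported without naming a device. The weekly questions are formally given to a research assistant. The exposed outcomes are secondary, in a 40-person pilot.

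Much of this stands. It rules out several stronger readings that a reader might draw:
- **That masking fails.** The documents show a risk, not a failure.
- **That all outcomes are affected.** The images, including the primary structure outcome, are read by others after the study.
- **That the coordinator certainly asks the weekly questions.** That is an inference from sections that disagree.
- **That unmasking stays within the traction arm.** First disclosures are likelier there, but a known label would carry the information to both arms.

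What does not stand is that the safeguards close the gap. None of them prevents a trap from being named in an answer, an adverse event description, a withdrawal reason or a log entry that the coordinator handles.

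**Conclusion.** The concern holds as a conflict of roles. The person who must remain masked for the symptom and function assessments also receives, records, downloads and transcribes information that can reveal the orthosis. The sections on who asks the weekly questions (5.5, 6.10, 8.7.g) and who sees the A/B label (6.2, 6.3, 10.7.a) must be reconciled.

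The bias risk is mainly to dexterity, grip, pinch and tenderness at weeks 4, 12 and 24, and its direction is unknown. The statement that first disclosures are likelier in the traction arm rests on the trap-specific complaints being listed for that group only. The statement that both arms could be unmasked rests on the coordinator knowing the labels, as 6.3 says. No disclosure percentage should be reported as expected. The change should be made, but the point does not undermine the primary VAS or the imaging outcomes in the same way.

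**What to change.** - **6.10, 5.5 and 8.7.g:** name one route for the weekly contact. Let the coordinator send only the reminder. Collect items 3, 5 and 8 by automated REDCap survey or through existing non-assessor staff such as the OT, who is already unmasked and already the contact for orthosis problems. Add the request not to disclose to each weekly contact.
- **8.7.b, 8.7.g, 7.1, 7.2 and 10.10.b:** have adverse event details and withdrawal or early-termination reasons taken by the same route. Clinical grading and reporting lines need not change.
- **6.2, 6.3, 10.7.a and 10.10.b:** hide those fields and the A/B label from the coordinator's REDCap role and downloads, and withhold them from the coordinator at the weekly meeting. Make the allocation sections agree.
- **10.10.b:** have logs keyed by a non-assessor, or by the coordinator only after the last participant's week-24 assessment. Reconcile the return visit (24 weeks or 24 months).
- **6.9:** record the assessor's guess at weeks 4, 12 and 24.

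The cost is protocol wording, REDCap permissions and some OT time, with no new staff. The small downside is that the first intake of device problems may be by an unmasked person.

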**1.1 Schedule of Activities (SoA)*****The schedule below is what is planned for our participants.***

Procedures	-4	Screening Visit - Day -30 to -1	Enrollment/Baseline Visit 1, Day 1 +/-7 days	Reminder Visit 1, Day 7 +/-3 days	Study Visit 2, Day 14 +/- 7 days	Reminder Visit 2, Day 21 +/- 3 days	Study Visit 3, Day 28 +/- 7 days	Reminder Visit 3, Day 35 +/- 3 days	Reminder Visit 4, Day 42 +/- 3 days	Reminder Visit 5, Day 49 +/- 3 days	Reminder Visit 6, Day 56 +/- 3 days	Reminder Visit 7, Day 63 +/- 3 days	Reminder Visit 8, Day 70 +/- 3 days	Reminder Visit 9, Day 77 +/- 3 days	Reminder Visit 10, Day 84 +/- 14 days	Reminder Visit 11, Day 98 +/- 3 days	Reminder Visit 12, Day 105 +/- 3 days	Reminder Visit 13, Day 112 +/- 3 days	Reminder Visit 14, Day 119 +/- 3 days	Reminder Visit 15, Day 126 +/- 3 days	Reminder Visit 16, Day 133 +/- 3 days	Reminder Visit 17, Day 140 +/- 3 days	Reminder Visit 18, Day 147 +/- 3 days	Reminder Visit 19, Day 154 +/- 3 days	Reminder Visit 29, Day 161 +/- 3 days	Final Study Visit, Day 168 +/- 14 days
Week	0																									
Screening Questionnaire	X																									
Eligibility Assessment	X																									
Baseline Demographics	X																									
Randomization	X																									
Create either the traction v resting hand orthosis	X																									
Repeated measures evaluation	X						X																			X
Hand photographs	X						X																			X
PA Radiographs	X																									X
MRI Screener	X																									X
Serum creatinine a	X																									X
Urine Pregnancy test b	X																									X
Proof of Concept Radiographs c						X																				
MRI of the most symptomatic DIP joint c					X																					X
Weekly Reminders (telephone, text, or email)		X	X	X	X	X	X	X	X	X	X	X	X	X	X	X	X	X	X	X	X	X	X	X		
Adverse Event and Review		X	X	X	X	X	X	X	X	X	X	X	X	X	X	X	X	X	X	X	X	X	X	X		
Final Visit Assessment Questions																										X

**Table 1. Schedule of Activities.**a Only for those being screened for MRIb Only for those of childbearing age who are womenc Only for a selected group of 10 participants

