#### 8.7.b Adverse Event Reporting

Our Research Coordinator will assess for adverse events systematically at each in clinic visit. If an adverse event is detected, he will contact [name] to complete adverse event(s) form(s) at each of those visits where the details of such adverse events will be recorded in RedCap. Additionally, should any adverse events be reported to our Research Coordinator between in clinic visits, all those events will also be recorded in RedCap by [name].

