#### 8.7.g Time period and frequency for event assessment and follow up.

The occurrence of an adverse event (AE) or serious adverse event (SAE) may come to the attention of study personnel during study visits and interviews of a study participant presenting for medical care, or upon review by a study monitor.

All AEs including local and systemic reactions not meeting the criteria for SAEs will be captured on the appropriate case report form (CRF) in RedCap. Information to be collected includes event description, time of onset, [name] assessment of severity, relationship to traction versus standard orthosis, and time of resolution/stabilization of the event. All AEs occurring while on study must be documented appropriately regardless of relationship. All AEs will be followed to adequate resolution. For an expected AE, follow up for 30 days after the onset of the AE will be considered as an adequate resolution.

Any medical condition that is present at the time that the participant is screened will be considered as baseline and not reported as an AE. However, if the study participant's condition deteriorates at any time during the study, it will be recorded as an AE.

Changes in the severity of an AE will be documented to allow an assessment of the duration of the event at each level of severity to be performed. AEs characterized as intermittent require documentation of onset and duration of each episode.

Our Research Coordinator, [name], will record all reportable events with start dates occurring any time after informed consent is obtained until 7 (for non-serious AEs) or 30 days (for SAEs) after the last day of study participation. At each study visit (including in clinic visits and weekly telephone calls), the investigator will inquire about the occurrence of AE/SAEs since the last visit. Events will be followed for outcome information until resolution or stabilization.

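### Sections 8.7.g and 1.1 intend all-cause adverse event inquiry at every clinic visit and weekly contact, but 8.7.b and the weekly script in 6.10 do not deliver it between clinic visits.

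*Combined protocol and SAP*

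**What the plan says.** Three sections of the combined protocol and SAP, and one row of its schedule, bear on how adverse events are found.

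- **Section 8.7.g** sets frequency and scope: "At each study visit (including in clinic visits and weekly telephone calls), the investigator will inquire about the occurrence of AE/SAEs". On scope it says: "All AEs occurring while on study must be documented appropriately regardless of relationship".
- **Section 1.1, Schedule of Activities**, has a row named "Adverse Event and Review". The column alignment is broken in the text available, but the marks run across the weekly contacts, in line with 8.7.g.
- **Section 8.7.b** says: "Our Research Coordinator will assess for adverse events systematically at each in clinic visit". For the time between, it says: "should any adverse events be reported to our Research Coordinator between in clinic visits, all those events will also be recorded in RedCap".
- **Section 6.10** gives the only weekly question list in the document. It has eight items, and staff are to "contact participants on a weekly basis via participants' preferred method of contact: email, text or phone". The only item that leads to an adverse event form is the eighth: "Have you had any problems with the orthosis".

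Section 8.7.a defines adverse events without regard to cause. Sections 8.7.c and 8.7.d leave severity to the study clinician and require a clinician to document another cause before an event is classed as not related.

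**The concern.** The rule in 8.7.g and the tool in 6.10 differ in scope. A participant who answers item 8 as written must first decide whether the orthosis caused the problem. If the answer is no, no form follows and the clinician never sees the event. That makes the participant the first judge of causality, a task that 8.7.d gives to the clinician.

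This matters more here than in many trials. The expected events in 8.7.e include increased hand pain and numbness or tingling, and 5.3 admits only people who already have frequent finger joint pain of at least 40 on a 0 to 100 scale. Worse hand pain is easily put down to the arthritis. A hospital stay is even less likely to be called an orthosis problem, yet 10.7.a undertakes to establish whether a hospitalisation is related to taking part, and no weekly item asks about one.

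Other provisions rely on the same information. Section 8.7.g wants onset and duration for each intermittent episode, and these are hard to recall over many weeks. Section 8.7.h starts its 48-hour notice of serious events from the time of awareness and sets an ad hoc review trigger at more than 10 serious events. Section 10.10.a has the study team review safety findings weekly. Each is only as complete as the asking behind it.

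**Working it through.** No sample size, power or event-rate figure is involved, and the plan states no figure to reproduce. The check sets the sections side by side and then measures the intervals between clinic visits.

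**Comparison**

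| Source | When asked | Scope | Who asks |
|---|---|---|---|
| 8.7.g | Clinic visits and weekly calls | All causes | Investigator |
| Schedule, 1.1 | Marked across the weekly contacts | Not restricted | Not stated |
| 8.7.b | Systematically at clinic visits; reports recorded in between | Not restricted | Research Coordinator |
| 6.10, item 8 | Weekly, by email, text or phone | Orthosis problems | Research assistant |

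Sections 8.7.g and 1.1 agree. Section 8.7.b is silent on active inquiry between visits. Section 6.10 makes the weekly contact but asks a narrower question. Section 8.7.g also assumes a telephone call, whereas 6.10 allows email or text, where nobody is on the line to probe.

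**Inputs.** Clinic visits are at baseline and weeks 2, 4, 12 and 24 (4.3.a). Days and windows come from 1.1: day 1 ± 7, day 14 ± 7, day 28 ± 7, day 84 ± 14 and day 168 ± 14. The schedule labels day 84 a reminder visit, but 4.3.a lists week 12 as a study visit with outcome assessments, so it is counted as a clinic visit.

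**Formulas.** Nominal gap = next day − previous day. Longest gap within windows = (next day + its window) − (previous day − its window).

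| Interval | Nominal | Longest within windows |
|---|---|---|
| Baseline to week 2 | 14 − 1 = 13 days | 21 − (−6) = 27 days |
| Week 2 to week 4 | 28 − 14 = 14 days | 35 − 7 = 28 days |
| Week 4 to week 12 | 84 − 28 = 56 days (8 weeks) | 98 − 21 = 77 days |
| Week 12 to week 24 | 168 − 84 = 84 days (12 weeks) | 182 − 70 = 112 days (16 weeks) |

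**Contacts inside the two long gaps.** The schedule places 7 reminder contacts between day 28 and day 84 (days 35 to 77) and 10 between day 84 and day 168 (days 98 to 161). Under 8.7.g each is an all-cause inquiry, so the scheduled interval is 7 days, except for 14 days from day 84 to day 98 because no day 91 contact is listed. Under the 6.10 script each of these 17 contacts asks only about the orthosis.

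**The case against.** The strongest reply is that the protocol already has a governing rule. Section 8.7.g is the section on frequency of assessment, the schedule agrees with it, and staff who follow both ask about all events every week. Section 8.7.b never says that inquiry is confined to clinic visits and can be read together with 8.7.g. Section 6.10 concerns compliance and does not claim to replace the safety inquiry. Items 3 and 5, on why the orthosis was not worn, may bring out an illness or hospital stay. Section 8.7.g names further routes, such as presentation for medical care and monitor review. Section 10.7 has participants with skin, nerve or circulation complaints in trapped fingers contact the occupational therapist. The manual of procedures, which is not available here, may add a prompt.

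Much of this stands, and it limits the point. The gap arises only if staff work from 8.7.b and the script. It does not remove the point, because the only weekly questions written down do not carry out the 8.7.g inquiry and the routes listed are indirect or depend on the participant.

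Three stronger readings are tempting, and the documents do not support them:

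- A reader might infer that a serious event could reach the Safety Officer months late with every written rule obeyed. It could not: leaving out the weekly inquiry would itself breach 8.7.g and depart from the schedule.
- A reader might infer that event rates by arm depend on which section is followed. Finger traps might prompt more orthosis complaints than a resting splint, but both arms get the same questions, section 9.0 plans no comparison of event rates, and 10.10.a mentions group comparisons only if needed. Nothing in the documents quantifies a differential effect.
- A reader might take 112 days as the expected delay. It requires week 12 on its earliest day, week 24 on its latest and no spontaneous report in between.

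**Conclusion.** The inconsistency is real and should be corrected, as a harmonisation of existing rules and not as a flaw in the design. The intended design, weekly all-cause inquiry, is already stated in 8.7.g and the schedule. The 6.10 script does not deliver it, and 8.7.b does not call for it.

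The exposure is 8 weeks and then 12 weeks between clinic visits, with 112 days as the outer limit. It applies to events that the participant does not attribute to the orthosis and does not volunteer. These are intervals without a general question, not counts of missed events; the documents give no basis for such a count. The conclusion assumes that the eight items are used as written, that nothing in the manual of procedures adds a general question, and that week 12 is attended in clinic.

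**What to change.** 1. In 6.10, reword weekly item 8 to be cause-neutral: *Since our last contact, have you had any new or worse health problem, hospital stay or emergency visit, whether or not you think it is related to the orthosis?* A yes leads to an adverse event form. The wording suits email and text as well as telephone.
2. In 8.7.b, extend systematic assessment to read *at each in-clinic visit and each weekly contact*, so that it matches 8.7.g.
3. Leave relatedness with the study clinician under 8.7.d. While editing, state consistently in 6.10, 8.7.b and 8.7.g who asks and by what means.

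The cost is one reworded item and one amended sentence, with no added visit, contact or form. The downside is more unrelated events to record and review, which 8.7.g already requires.
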